14.6.4. Change from Baseline

Definition	Reporting Details
Change from Baseline	= Post-Dose Visit Value – Baseline
% Change from Baseline	= 100 x [(Post-Dose Visit Value – Baseline) / Baseline]
Ratio to Baseline ^[1]	= Post-Dose Visit Value / Baseline

NOTES: Refer to Section 5.2 for definition of Baseline. Unless otherwise stated, if Baseline or the Post-Dose value is missing the result will be set to missing.

[1] For log_e transformed data Ratio to Baseline is the back transformed change from baseline value

14.6.5. Efficacy

Assigning the worst score for subjects with surgery or missing data
Relevant efficacy endpoints

 Subjects who undergo surgery/sinuplasty will have their worst observed score (or worst observed 4-week mean) assigned for all subsequent visits (or 4-week periods) following surgery/sinuplasty. The assigned value will be the worst observed value from baseline up to before the surgery/sinuplasty. Assessments taking place on the same day as surgery/sinuplasty are assumed to have been carried out before the surgery/sinuplasty. Subjects who have not experienced surgery/sinuplasty and have missing values due to study withdrawal, will have their worst observed score (or worst observed 4-week mean) assigned for all missing visits (or 4-week periods) following study withdrawal. The assigned value will be the worst observed value from baseline up until study withdrawal. Subjects with missing data for other reasons will have their worst observed score (or worst observed 4-week mean) prior to the missing visit (or missing 4-week period) assigned.
Total Endoscopic Nasal Score
Responder

 A responder will be defined as a participant with a ≥1-point improvement from baseline in total endoscopic nasal score (centrally read). Participants with no improvement/worsening or with missing data will be considered a non-responder for analysis.
VAS scores (individual and composite)
Individual VAS Scores

 VAS scores are captured electronically using an eDiary. participants indicate their response on a line CCI - This section contained Clinical Outcome Assessment data collection questionnaires or indices, which are protected by third party copyright laws and therefore have been excluded. The final VAS scores for inclusion in summary and analysis tables will be derived from the electronically captured score by CCI.
Change from baseline categories

 The baseline scores will be calculated as the mean of the scores reported between the 7 days prior to the first dose. The scores for each 4-week period will be calculated as the mean of the scores reported between timepoints detailed in Section 14.3.3.
Composite VAS scores

VAS scores (individual and composite)

- Two separate composite VAS scores will be derived using the final VAS scores:
- Composite of nasal obstruction, nasal discharge, mucus in the throat and loss of smell
 - CCI [REDACTED]
- Composite of nasal obstruction, nasal discharge, mucus in the throat, loss of smell and facial pain
 - CCI [REDACTED]

Nasal Surgery (reported on the disease related events page of the eCRF)
Time to first nasal surgery

 Calculated as (Date of first nasal surgery – Date of first dose of study treatment) + 1 Analysis excluding data from the follow-up period after Week 52: For participants who withdraw from the study before Week 52 and before experiencing surgery, event times will be censored at the time of study withdrawal For participants who complete to Week 52 without experiencing surgery, event times will be censored at the time of the Week 52 visit. Analysis including data from the follow-up period after Week 52: For participants who withdraw from the follow-up period before completion and before experiencing surgery, event times will be censored at the time of study withdrawal. For participants who complete the follow-up period without experiencing surgery, event times will be censored at time of completion of follow-up.
Need for surgery

 Need for surgery at Week 52 is based on the overall VAS symptoms score and the endoscopic NP score (centrally read). Participants will be classified as having a need for surgery if they meet the following: 
 Overall VAS symptoms score >7 (Weeks 49-52) and total endoscopic NP score ≥5 (Week 52, centrally read) Participants who have undergone nasal polyps surgery at any time prior to the week 52 visit, or who have a missing endoscopic NP score (centrally read) at Week 52, or missing overall VAS symptom score (Weeks 49-52) will be identified for analysis as still having a need for surgery.
Rate of surgery

 The crude rate of surgery will be presented for each treatment arm, this will be calculated as: $\left(\frac{\text{Total number of nasal surgeries}}{\text{Total number of days in the study}} \right) * 365.25$

Systemic steroid use
Conversion of glucocorticoid dose to mgs of prednisolone equivalent OCS use

 The total number of mgs of prednisolone equivalent OCS use per year will be calculated as follows and will be based on systemic steroids taken via the following routes: Oral, Intravenous, Intramuscular: $\left(\frac{\text{Total cumulative mgs prednisolone – equivalent OCS use in period}}{\text{Total number of days in period}} \right) * 365.25$ 
 The following table from the study reference manual will be used for conversion of intravenous and oral steroid use into prednisolone equivalent OCS use in mgs:

Systemic steroid use	
Glucocorticoid	Approximate equivalent dose (mg)
Short-Acting	
Cortisone	25
Hydrocortisone	20
Intermediate-Acting	
Methylprednisolone	4
Prednisolone	5
Prednisone	5
Triamcinolone	4
Long- Acting	
Betamethasone	0.6-0.75
Dexamethasone	0.75

- Participants who withdraw early from the study will have yearly use estimated based on use during the study.

Courses of Therapy

- A course of systemic steroid therapy is defined by the start and stop date of therapy.
- If the start date of a course of systemic steroid therapy occurs <7 days from the stop date of the previous course, it will be considered a continuation of the same course.

Days on Therapy

- The duration of a course of systemic steroids will be calculated as the number of days between the start and stop date of the course: stop date – start date + 1
- For each participant the total number of days on systemic steroids will be calculated as the sum of the duration of each of their courses of therapy.
- For each participant the percentage of days on systemic steroids will be calculated as follows:

$$\left(\frac{\text{Total number of days on systemic steroids}}{\text{Total number of days in the study}} \right) * 100$$

Nasal Surgery or Course of Systemic Steroids

Time to first nasal surgery or course of systemic steroids

- Calculated as (Date of first nasal surgery/course of systemic steroids – Date of first dose of study treatment) + 1
- Analysis excluding data reported in the follow-up period after Week 52:
For participants who withdraw from the study before Week 52 and before experiencing either event, event times will be censored at the time of study withdrawal
For participants who complete to Week 52 without experiencing either event, event times will be censored at the time of the Week 52 visit

Antibiotic Use
Courses of Therapy

 A course of antibiotics is defined by the start and stop date of therapy. If the start date of a course of antibiotics occurs <7 days from the stop date of the previous course, it will be considered a continuation of the same course.

SNOT-22														
SNOT-22 Total Score														

 Each question of the SNOT-22 is graded on a [redacted] CCI. The scores for each of the questions will be summed to derive [redacted] CCI [Hopkins, 2009]. CCI - This section contained Clinical Outcome Assessment data collection questionnaires or indices, which are protected by third party copyright laws and therefore have been excluded. If a participant does not complete any questions at a visit the total score for that visit will be missing. If a participant has some (but no more than 50%) missing responses to questions at a visit, then the missing responses will be imputed with the unrounded mean of the non-missing responses at that visit. The SNOT-22 total score for that visit will then be rounded to the nearest integer. 														
SNOT-22 Responder														

 A responder is defined as having a ≥ 8.9-point improvement (decrease) from baseline in SNOT-22 total score. 														
SNOT-22 Domain Scores														

 The six SNOT-22 domain scores are shown below; the domain scores are derived from the sum of the individual item-scores shown [Health Outcomes Study, 2018]: 
  
 Domain	Items/Questions	
   
 Nasal	CCI - This section contained Clinical Outcome Assessment data collection questionnaires or indices, which are protected by third party copyright laws and therefore have been excluded.	
 
 Non-nasal symptoms		
 
 Ear/facial symptoms		
 
 Sleep		
 
 Fatigue		
 
 Emotional consequences		
  
	Domain	Items/Questions	Nasal	CCI - This section contained Clinical Outcome Assessment data collection questionnaires or indices, which are protected by third party copyright laws and therefore have been excluded.	Non-nasal symptoms		Ear/facial symptoms		Sleep		Fatigue		Emotional consequences	
Domain	Items/Questions													
Nasal	CCI - This section contained Clinical Outcome Assessment data collection questionnaires or indices, which are protected by third party copyright laws and therefore have been excluded.													
Non-nasal symptoms														
Ear/facial symptoms														
Sleep														
Fatigue														
Emotional consequences														

UPSIT
UPSIT total score

 The total score is calculated as the number of times the correct smell is identified out of a possible 4 choices, for 40 different smells.

Work Productivity and Activity Impairment Questionnaire (WPAI)

- The following summary variables will be derived from the 6 WPAI questions:

Summary variable	Derivation
CCI - This section contained Clinical Outcome Assessment data collection questionnaires or indices, which are protected by third party copyright laws and therefore have been excluded.	
[Redacted content]	

ACQ-5**ACQ-5 Score**

- ACQ-5 is a 5-item questionnaire developed as a measure of patient's asthma control. Response options for each question are on CCI [Redacted]
- The questions are equally weighted, and the ACQ-5 score is calculated as the mean of the 5 questions, CCI [Redacted]
- For a given visit, if the response to one of the 5 questions is missing then the ACQ-5 score will be calculated as the mean of the available responses. If the response to more than one question is missing, then the ACQ-5 score will be set to missing.

Asthma exacerbations**Clinically significant asthma exacerbation**

- A clinically significant asthma exacerbation is defined as a worsening of asthma requiring systemic steroids (i.v. or oral) for at least 3 days or a single intra-muscular corticosteroid dose, and/or an ED visit and/or hospitalisation.

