### 9.2.4. Medication

The number of courses of systemic steroids and OCS as well as the dose and duration of the courses will be recorded in the CRF. The dose for a course of OCS will be according to the participants SoC for OCS use for its NP condition. The dose and duration of the OCS taken will be recorded in the eCRF. For the purpose of this study a course of

systemic corticosteroid is considered continuous if treatment is separated by less than 7 days. The methodology to convert various doses of intravenous and oral steroids to prednisolone-equivalent OCS will be provided in the SPM.

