
 To further evaluate the efficacy of 100mg mepolizumab compared to placebo 	
 Percentage of participants classified as responders according to a 1 point or greater decrease from baseline in NP Score at Week 52 (based on centrally ready data). Change from baseline in mean individual VAS symptom scores for nasal discharge, mucus in the throat, and facial pain during the 4 weeks prior to Week 52. Change from baseline in the mean composite VAS score (combining VAS scores for nasal obstruction, nasal discharge, mucus in the throat, loss of smell and facial pain) during the 4 weeks prior to Week 52. Change from baseline in UPSIT at Week 52. Change from baseline in PnIF at Week 52.

 To evaluate the impact on quality of life of 100mg mepolizumab compared to placebo 	
 Percentage of participants classified at Week 52 as responders according to an 8.9 point or greater decrease from baseline in SNOT-22 total score. Change from baseline in SNOT-22 domain scores at Week 52.

 To further evaluate the impact on 	
 Rate of nasal surgery up to Week 52.

CONFIDENTIAL

2020N427698_00

205687

Objectives	Endpoints

requirement for nasal surgery of 100mg mepolizumab compared to placebo
	
 • Time to first inclusion on waiting list for NP surgery up to Week 52. • Percentage of participants who are included on waiting list for NP surgery. • Percentage of participants classified as 'need for surgery' responders according to NP score (based on centrally read data) and overall VAS symptom score.

 • To evaluate exploratory biomarkers of nasal polyposis and response to 100mg mepolizumab compared to placebo 	
 • Evaluate exploratory blood biomarkers (including blood eosinophils) on response to mepolizumab.

 • To evaluate the impact on health outcomes of 100mg mepolizumab compared to placebo 	
 • Change from baseline in SF-36 Mental Component Summary (MCS), Physical Component Summary (PCS) and 8 summary scores at Week 52. • Change from baseline in WPAI Questionnaire at Week 52.

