14.7. Appendix 7: Reporting Standards for Missing Data

14.7.1. Premature Withdrawals

Element	Reporting Detail
General	
 • The protocol objective is to collect data over the full study treatment period (up to Week 52) for all participants, whether they continue on interventional product (IP) and complete Week 52 on-treatment, or whether they withdraw prematurely from IP. 
 ○ For the participants who withdraw prematurely from IP before Week 52 and agree to the continued collection of data off-treatment, data will be collected for up to 52 weeks after randomization (or up to 76 weeks if the participant enters the Follow-up period after Week 52) either through clinic visits or via phone contact, in accordance with the participants existing visit schedule. ○ Where available, off-treatment data will be included in the analysis of the co-primary endpoints and, unless otherwise indicated, in the analysis of other efficacy endpoints. • A participant will be considered to have completed study treatment if he/she continues to take study treatment until Visit 14 (Week 48) and completes Visit 15 (week 52). • As specified in the protocol participants will be considered to have completed the study upon completion of Visit 15 (Week 52) regardless of whether they continue to take IP. • A participant eligible for the no-treatment follow-up will be considered to have completed follow-up if they continue to participate in the study until Visit 18 (Week 76) • All available data from participants who were withdrawn from the study will be listed and all available planned data will be included in summary tables and figures, unless otherwise specified. • Withdrawal visits will be slotted as per Appendix 3: Assessment Windows or will be summarised as withdrawal visits.
Pre-Screen/Screen and Run-in Failures	
 • Participants are assigned a subject number at the time of signing informed consent. • Pre-Screen Failure: A participant who is assigned a subject number but did not continue through to Visit 1. • Screening Failure: Participant performs a Visit 1 procedure, but does not enter the run-in period • Run-in Failure: Participant enters the run-in period, may perform a Visit 2 procedure, but is not subsequently randomised.

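### Days on systemic steroids includes the untreated gap inside merged courses, and the day-count denominator it shares with the surgery rate needs a definition

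*SAP*

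**What the plan says.** SAP Section 14.6.5 (Systemic steroid use) builds the day count in three steps.

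- **Merging.** The trigger reads: "If the start date of a course of systemic steroid therapy occurs <7 days from the stop date of the previous course". A restart inside that limit is joined to the earlier course and does not count as a new one. Protocol Section 9.2.4 has a similar convention: "systemic corticosteroid is considered continuous if treatment is separated by less than 7 days".
- **Duration.** A course lasts the "number of days between the start and stop date of the course", with the formula stop − start + 1.
- **Total.** Per participant, "the total number of days on systemic steroids will be calculated as the sum of the duration of each of their courses".

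The percentage of days on steroids divides that total by "Total number of days in the study". The crude rate of surgery in the same section has the same denominator. The milligrams-per-year formula, also in 14.6.5, divides by days in the period instead.

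Both summaries are Week 52 endpoints. SAP Section 2.1 lists "Rate of nasal surgery up to Week 52" and sets the same horizon for days on steroids. The opening of SAP Section 7 limits Sections 7.1 to 7.4 to data up to Week 52, and the footnotes of Tables 2.46 (surgery rate) and 2.53 (steroid days) repeat the limit.

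The documents are not uniform on when the study ends. Protocol Section 6.4 and SAP Section 14.7.1 treat it as complete at Visit 15 (Week 52). SAP 14.7.1 also says: "A participant eligible for the no-treatment follow-up will be considered to have completed follow-up if they continue to participate in the study until Visit 18". Protocol Section 5.3 puts the final study visit at Week 76 for up to the first 200 randomised.

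**The concern.** Merging nearby courses is sensible when the question is how many courses a participant had. When the question is how many days were spent on steroids, a merged course runs from the first start to the last stop and so takes in days without drug. No line in the SAP deducts them. The error goes one way, upwards, and only for participants who restart soon after stopping. It passes into the percentage of days, which uses the same numerator.

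The second matter is the denominator. Surgeries and steroid days are cut at Week 52, but the person-time is written as days in the study, which is never defined. Someone programming from that line alone could include the drug-free follow-up for participants who entered it. Absolute annual rates would then be too low, and individual percentages would not be comparable between participants who were followed up and those who were not.

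**Working it through.** The plan gives no figure to reproduce here, so the check applies its rules to dates.

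**Numerator.** Let the first course stop on day *e* and the next start on day *s*. The SAP merges when *s* − *e* < 7, so for separate courses *s* − *e* runs from 1 to 6. Untreated days in the gap = *s* − *e* − 1, that is 0 to 5 per merge. If the protocol's wording is read as fewer than 7 drug-free days, the upper limit is 6. Successive merges add up.

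Examples at the largest gap that still merges (course lengths are assumed):

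| Courses | Merged: stop − start + 1 | Days dosed | Excess |
|---|---|---|---|
| Day 1–5 and Day 11–15 | 15 − 1 + 1 = 15 | 5 + 5 = 10 | 5 (+50%) |
| Day 1–7 and Day 13–19 | 19 − 1 + 1 = 19 | 7 + 7 = 14 | 5 (+36%) |

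When the second course starts the day after the first stops (*s* − *e* = 1), the merged and dosed totals agree.

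Percentage of days for the first example over 52 × 7 = 364 days: 15/364 = 4.12%, against 10/364 = 2.75% on dosed days.

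**Denominator, if follow-up were counted.** Follow-up adds 24 × 7 = 168 days, giving 532 days to Week 76.

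- One follow-up completer: 364/532 = 0.684, so a fixed Week 52 numerator gives a value 31.6% too low.
- All 400 planned participants, each observed to Week 52, with 200 followed to Week 76: mean days = (200 × 364 + 200 × 532)/400 = 448, and 364/448 = 0.8125, so the pooled rate is 18.8% too low.
- Illustration per arm, assuming one surgery per operated participant at the planning proportions in Protocol Section 10.1 (40% and 25% of 200, or 80 and 50 surgeries) and 100 per arm followed to Week 76: 80/72,800 × 365.25 = 0.401 and 50/72,800 × 365.25 = 0.251 per year. On 89,600 days these become 0.326 and 0.204.
- The ratio of the two rates is 0.625 either way. With an assumed split of the 200 follow-up participants of 90/110 or 110/90 between arms, it moves to about 0.60 or 0.65.

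**Both effects together.** For the first example in a follow-up completer, 15/532 = 2.82% against 10/364 = 2.75%. The two effects pull in opposite directions on the percentage of days.

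**The case against.** On the numerator, the best reply is that merging is a pre-specified convention shared with the protocol, applied equally to both arms, and that measuring a continuous course from end to end follows from it. That stands as a definition of a course. It does not make an untreated day a treated one, and the quantity displayed is days on steroids. It is also fair that +50% needs two short courses at the widest gap that still merges, and that the documents do not say how often participants restart so soon.

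On the denominator, a reader might infer that it does include the 24-week follow-up for the first 200 participants, and so that the percentage of days and the surgery rate are understated. The documents do not support that as a finding. The opening of SAP Section 7, the footnotes of Tables 2.46 and 2.53, and study completion at Visit 15 all point to a Week 52 cut. The follow-up displays (Tables 2.63 to 2.69) contain neither measure, so the formulas serve Week 52 displays only. Against this, SAP Section 7.5 includes follow-up data in participants' time in the study, SAP Section 14.6.3 computes follow-up duration from a study end date later than Week 52, and Protocol Section 5.3 runs to Week 76. The footnotes limit the data reported without defining person-time. What remains is an undefined term.

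**Conclusion.** The numerator point holds on the text. As written, days on systemic steroids and its percentage include up to 5 untreated days per merge, for participants who restart less than 7 days after stopping and for no others. The average effect cannot be sized without the frequency of such restarts. The number of courses, the secondary endpoint of requiring any systemic steroid, and milligrams per year do not use this day count.

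The denominator point is an alignment matter. The 31.6% and 18.8% figures are ceilings: they assume that follow-up is counted, that everyone is observed to Week 52, and that a full 200 are followed to Week 76, whereas the protocol says up to 200. It would also go too far to say that the percentage of days comes out understated: with a Week 52 denominator it is overstated for anyone with gap days, and if follow-up were counted the two effects would partly or wholly cancel for such participants. Entry to follow-up depends on order of randomisation and not on arm, so the comparison between arms would move little.

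Both measures are descriptive 'other' endpoints without a test (SAP Sections 7.3.6 and 7.3.12.2) and outside the hierarchy in SAP Section 5.5. Type I error and power are not affected. This is a minor correction.

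**What to change.** Make two edits in SAP Section 14.6.5.

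1. **Days on Therapy.** Define total days as the number of distinct calendar days covered by the union of the recorded start–stop dosing intervals. State that the less-than-7-day merging applies only to counting courses.
2. **Percentage of days and crude surgery rate.** Replace the undefined denominator in both formulas with days from first dose to the earlier of the Week 52 visit or study withdrawal. Follow-up time then cannot enter, and numerator and denominator share one window.

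The cost is two derivation lines and the matching dataset specification. Protocol Section 7.6 already requires start and end dates for all medication, so no new data are needed. The second edit is worth making even if a Week 52 cut was always intended.
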